**Palatal Wound Healing Evaluation After
Application of Platelet Rich Fibrin Versus 0.2%
Hyaluronic Acid Dressings
(Randomized Controlled Clinical Trial)**

Methodology

Date: 12/5/2020

Sample selection and assignment:

Thirty patients (16 females and 14 males) who were candidates for free gingival grafting surgery participated in this prospective clinical trial.

The subject were recruited consecutively from the outpatient clinic of Oral Medicine, Periodontology, oral Diagnosis and Radiology Department, Faculty of Dentistry, Ain Shams University .The purpose of the study was explained to all patients and an informed consent was signed before the conduction of the study. The proposal was presented to the faculty of Dentistry Ain Shams University Research Ethics committee and was approved before starting the research with number (566). Also the study was registered in clinical trial registration site (NCT).

Patient selection:

Inclusion Criteria:

- Patients who were indicated for soft tissue augmentation with free gingival graft for mucogingival surgery or for implant therapy.

Material and Method

- Age range (20-50) years.
- Good patient compliance with the plaque control instructions following initial therapy.

Exclusion criteria:

- Presence of systemic diseases which could influence the outcome of the therapy.
(American Society of Anesthesiologists I; ASA I)
- Smoker patients.
- Pregnant and lactating females.
- Vulnerable group of patients (prisoners, handicapped, decisionally impaired individuals).

Grouping Criteria:

The study consisted of three groups; the number of patient in each group was determined by sample size calculation based upon the results of *Yildirim et al. 2017*. Using alpha level of 0.05 (5%) and β level of 0.20 (20%) i.e. power = 80%; the estimated minimum required sample size was approximately 10 cases in each group. Patients were randomly selected using computer generated randomization (www.randomizer.org). Allocation concealment was achieved using a sealed coded opaque envelope containing treatment of the subject

Group I(10 patients):

Patients received platelet rich fibrin as a palatal dressing after free gingival graft harvesting.

Group II(10 patients):

Patients received hyaluronic acid* gel 3-4 times per day as a palatal dressing after free gingival graft harvesting.

Group III(10 patients) (Control group) :

Patients received gel foam as a palatal dressing after free gingival graft harvesting

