*Gengiegel 0.2% oral gel 20ml Riceerfarma Milano Italy.

III- Assessments:

1-Clinical parameters:

- Subjective assessment**

-Patients were asked to assess their pain sensation and bleeding at 1st, 3rd, 7th 14th, 21st and 30th days using the visual analogue scale (VAS). The visual analogue scale score by Price et al 1983 for pain ranged from 0 (no pain) to 10 (severe pain), while bleeding was scored as 0(not present) and 1(present) (***Price et al.1983***).

- Objective assessment**

-The Healing index scale by ***Landry et al.1988*** was used to assess the palatal wound healing, where in this index tissue color, response to palpation, presence of granulation tissue presence of suppuration and epithelization of the incision margin were recorded.

-The color of the palatal mucosa was assessed by comparing it to the adjacent and opposite side by taking pictures and using the image J program at 3rd, 7th, 14th, 21st and 30th days (***Pei-Nan et al.2012***).

- The thickness of the palatal mucosa was measured preoperative and 4 weeks postoperative by a graduated periodontal probe.

Material and Method

[figure not shown]

Fig (1): Palatal thickness measurements at 3 different points the middle of 1st, 2nd premolar and 1st molar 7mm from the gingival margin

IV-Surgical protocol:

A) Pre surgical procedures

Scaling and root planning was done; oral hygiene instructions was given to the patient to follow them.

B) Surgical procedures

Group 1:

1. Anesthesia (Articaine HCL 4% containing epinephrine at a concentration of 1:100,000)[†] was administrated at to the palate where a free gingival graft was harvested.
2. Just prior to surgery a 10 ml intravenous blood was obtained from the median antecubital vein of the patient in order to be divided into two 5 ml glass tubes[‡] without additives to be [§]centrifuged immediately at 2700 revolutions per minute for 12 minutes or in one 10 ml glass test tube without additives were centrifuged immediately at 3000 revolutions per minute for 10 minutes at room temperature.

[†] Artinibsa 4% cartouches de 1.8ml ,inibisa dental.

[‡] Dry Vacutube, Biocon®, Brazil

[§] PRF CENTRIFUGE (Duo machine), UNSPSC code 41100000 (Ostralos Ltd, New Zealand)

Material and Method

3. Coagulation started immediately and three parts quickly appear in the tube: a packed red blood cell at the bottom, acellular plasma at top and the PRF clot in between.

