- Oral hygiene instructions was given , antibiotic (Augmentin^{†††} 1 gm every 12 hours, metronidazole^{§§§} 500 mg every 12 hours) , anti-inflammatory and analgesics(Brufen^{****} 400 every 12 hours) was prescribed for the patient and instructed to avoid brushing at the surgical site only rinsing with hot saline mouthwash.
- Patient was recalled for assessment and follow up, sutures was removed after 1 week.

^{†††} Augmentin 1gm,Medical union pharmaceuticals(MUP) Egypt under license from ,Glaxosmithkline

^{§§§}Flagyl 500 mg, sanofi Aventis Egypt under license of sanofi Aventis French

^{****} Brufen 400mg, Al kahira pharm. and chem.Ind.Co. under license from abbott laboratories

VI-Postoperative evaluation and assessment:

- Patients were asked to assess their pain sensation and bleeding at 1st, 3rd, 7th 14th, 21st and 30th days using the visual analogue scale (VAS). The visual analogue scale score by Price et al 1983 for pain ranged from 0 (no pain) to 10 (sever pain), while bleeding was scored as 0(not present) and 1(present).
- The Healing index scale by *Landry et al. 1988* was used to assess the palatal wound healing, where in this index tissue color, response to palpation, presence of granulation tissue presence of suppuration and epithelization of the incision margin were recorded.
- The color of the palatal mucosa was assessed by comparing it to the adjacent and opposite side by taking pictures and using the image J program at 3rd,7th, 14th, 21st and30th days.
- The thickness of the palatal mucosa was measured preoperative and 4 weeks postoperative by a graduated periodontal probe.

IV-Statistical analysis:

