Categorical data were presented as frequencies and percentages and were analyzed using chi square test. Numerical data were tested for normality using Shapiro-Wilk test and were presented as mean and standard deviation values. Parametric data were analyzed using one-way ANOVA followed by Tukey's post hoc test for intergroup comparisons and one-way repeated measures ANOVA followed by Bonferroni post hoc test for intragroup comparisons. Non-parametric data were analyzed using Kruskal-wallis test followed by pairwise comparisons utilizing Mann Whitney U test with Bonferroni correction for intergroup comparisons and Friedman's test of repeated measures followed by multiple pairwise comparisons utilizing Wilcoxon signed-rank test with Bonferroni correction for intragroup comparisons. The significance level was set at $p \leq 0.05$ within all tests. Statistical analysis was performed with IBM® SPSS® Statistics Version 26 for Windows.

® IBM Corporation, NY, USA.

®SPSS, Inc., an IBM Company.

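### The protocol names no primary outcome or day, so its 5% alpha, 80% power and 10 per group belong to no identifiable test, while every test is run at 0.05

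*Protocol*

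**What the plan says.** Under Grouping Criteria, the protocol says that "the number of patient in each group was determined by sample size calculation based upon the results of" a cited 2017 study, with alpha 0.05, and then: "power = 80%; the estimated minimum required sample size was approximately 10 cases in each group". It gives no outcome, day, effect size or standard deviation.

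The sections III-Assessments and VI-Postoperative evaluation and assessment list the measures without ranking them:
- Pain (0–10) and bleeding (0/1): "Patients were asked to assess their pain sensation and bleeding at 1st, 3rd, 7th 14th, 21st and 30th days using the visual analogue scale".
- Healing index: no assessment days given.
- Colour: compared with the adjacent and opposite side by "taking pictures and using the image J program at 3rd, 7th, 14th, 21st and 30th days".
- Thickness: "The thickness of the palatal mucosa was measured preoperative and 4 weeks postoperative by a graduated periodontal probe".

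IV-Statistical analysis compares the groups by "one-way ANOVA followed by Tukey's post hoc test for intergroup comparisons", or by Kruskal-Wallis followed by Mann-Whitney with Bonferroni. Categorical data go to chi-square. Days are compared within a group by repeated-measures ANOVA or Friedman, with Bonferroni post hoc tests. The section then sets one threshold: "The significance level was set at $p \leq 0.05$ within all tests".

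**The concern.** Alpha and power are properties of a particular test. Here a sample size is claimed at 5% and 80%, but no test is identified to which those figures apply.

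The corrections that are specified work inside a single comparison. Tukey, and Bonferroni after Kruskal-Wallis, handle the three pairs of groups once one three-group test is done. The other Bonferroni steps handle pairs of days within one group. Nothing covers the between-group tests across outcomes or across days.

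With no designated outcome, one favourable day among many could be presented as the trial's finding. Nothing in the document would show that it had not been planned.

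**Working it through.** **1. The plan's own figure.** The 10 per group cannot be reproduced, because no effect size or SD is given. It can only be inverted, at two-sided 0.05 (assumed; sidedness is not stated) and 80% power:
- Two groups, normal approximation: (1.960 + 0.842) × √(2/10) = 1.25 SD.
- Two groups, t-test: about 1.32 SD.
- Three-group ANOVA on 30 patients: effect size f of about 0.60.

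The protocol does not say which of these comparisons was sized, or on which measure.

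**2. Number of between-group tests.** One-way ANOVA and Kruskal-Wallis take one value per patient, so the natural reading is one three-group test per outcome and day. This is an inference.
- Numeric: pain 6 + colour 5 + thickness 1 = 12.
- Categorical: bleeding 6, making 18 in all.
- Not counted: the healing index (no stated days), the second colour reference side, and the separate thickness points (three sites).

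**3. Error rates.** Trials of 3 × 10 patients with no true effect were simulated, using normal data with equal correlation between the days of one outcome and equal correlation between outcomes. A false benefit means that the three-group test has p ≤ 0.05 and the post hoc test favours PRF or hyaluronic acid over control. The rank route uses 0.05/3 for each pair. The correlations are assumptions; the protocol gives none.

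| Setting (between days, between outcomes) | ANOVA/Tukey | Kruskal-Wallis/Mann-Whitney |
|---|---|---|
| One test | 1.7% | 1.2% |
| 12 tests (0, 0) | 18% | 13.5% |
| 12 tests (0.5, 0.3) | 14% | 10.8% |
| 12 tests (0.7, 0.5) | 10.8% | 8.7% |
| 12 tests (0.9, 0.5) | 8.0% | 6.5% |

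Check at independence, with unrounded single-test rates: 1 − (1 − 0.0166)^12 = 0.182 and 1 − (1 − 0.0123)^12 = 0.138. Both agree with the simulated row.

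Expected number of false-benefit tests per no-effect trial, whatever the correlation: 12 × 0.0166 = 0.20 (Tukey) and 12 × 0.0123 = 0.15 (rank).

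**4. Sensitivity.**
- Whole-number pain scores with an assumed late floor, rank route: 10.9% at (0.5, 0.3), and 6.9–13.3% over the range.
- Adding the 6 bleeding tests: 12–18% at (0.5, 0.3). This needs assumed bleeding rates and an assumed pairwise rule, since the plan gives no post hoc test for categorical data.
- The choice between routes by Shapiro-Wilk was not modelled; each route was run alone.

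**The case against.** The strongest reply is that this is an absence, and that other documents may fill it. A threshold of 0.05 per test is ordinary. A statistical analysis plan that is not shown could set a testing order that controls error with that threshold unchanged. The protocol also mentions a registration, which is not at hand and might name the primary outcome. This stands as far as multiplicity control goes: a missing testing order is not the complaint. It does not dispose of the point, because the protocol itself states a sample size and carries its own statistics section, and neither identifies the outcome the size was meant for.

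Three further objections are right and limit the claim:
- A reader might infer that the protocol lays down 12 or 18 between-group tests. It does not. It lists assessment days and types of test, and it does not say that the colour comparison gives one number per patient per day. The count is an inference.
- A reader might infer that this trial has a false-positive rate of up to 18%. The document does not support that. It contains no rule that one significant day means success, and the top of the range needs six pain scores from the same patient to be uncorrelated.
- A reader might infer that naming one outcome secures the stated 80% power. Without an outcome, effect size and SD, that cannot be known.

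**Conclusion.** The defect can be read directly from the text: no outcome or day is designated primary, and alpha, power and sample size attach to no named measure. This holds without any simulation.

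Its possible size is conditional. It assumes one between-group test per outcome and day, and a reader who takes any single favourable result as a benefit. On those terms about 11–14% of no-effect trials would show a benefit on the 12 numeric tests at correlations of 0.5 and 0.3. The range is about 7–18% over day correlations of 0 to 0.9 and outcome correlations of 0 to 0.5. One pre-named test gives 1.2–1.7%. These figures already include the plan's Tukey and Bonferroni steps. They describe what the wording leaves open, not what the sponsor has done.

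It should be fixed. The analysis can run as written, but it has no identifiable confirmatory test.

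**What to change.** In Grouping Criteria and IV-Statistical analysis, state the outcome and day on which 10 per group was calculated, for example:

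*The primary outcome is [outcome] at day [x], the measure used for the sample size. It is compared between the three groups once at 0.05. All other outcomes and days are exploratory, and no efficacy conclusion rests on an isolated significant day.*

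The sponsor must take the outcome and day from its own calculation record and show that they were fixed before outcome data were seen. This matters because the protocol describes enrolment in the past tense: "Thirty patients (16 females and 14 males) who were candidates for free gingival grafting surgery participated in this prospective clinical trial". Choosing a primary outcome after seeing data would not restore the 5% level. If prior specification cannot be shown, label all outcomes exploratory and attach the 80% power statement to no result.

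The cost is in claims, since no extra patients or visits are needed. All other outcomes and days lose confirmatory status, and without a record the trial makes no confirmatory claim at all. The effect size and SD behind the calculation should be given alongside the outcome, because without them the power of the named test still cannot be verified.
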